10.2 Analysis of Adverse Events

A treatment-emergent Adverse Event (TEAE) is defined as an adverse event with an onset date that is after the first dose of study drug, and no more than 30 days after the last dose of upadacitinib and placebo, and 70 days after the last dose of adalimumab.

Events where the onset date is the same as the study drug start date are assumed to be treatment-emergent, unless the study drug start time and the adverse event start time are collected and the adverse event start time is prior to the study drug start time. If an incomplete onset date was collected for an adverse event, the event will be assumed to be treatment-emergent unless there is other evidence that confirms that the event was not treatment-emergent (e.g., the event end date was prior to the study drug start date).

Adverse event data will be presented by SOCs and PTs using MedDRA Version 19.1 or most up to date version, which will be sorted in alphabetical order by SOC and PT.

10.2.1 Analysis of Adverse Events Prior to Protocol-Defined Treatment Switching

10.2.1.1 Adverse Events Overview

The number and percentage of subjects experiencing TEAEs will be summarized by treatment groups for the following AE categories.

- All TEAEs
- Treatment-emergent serious adverse events (SAEs)
- Treatment-emergent severe adverse events
- TEAEs with a reasonable possibility of being related to study drug
- TEAEs leading to discontinuation of study drug
- TEAE leading to death
- Deaths (includes all deaths treatment-emergent and non-treatment-emergent)

In the AE overview summary, any event with an unknown severity will be considered as severe and any AE with an unknown relationship will be considered as having "reasonable possibility" of being related to study drug. Additional AE summaries may be considered for tabulation/summary based on recommendations from Clinical and Safety as deemed appropriate.

10.2.1.2 Adverse Events by System Organ Class and Preferred Term

The number and percentage of subjects experiencing adverse events a will be tabulated by SOC and MedDRA PT by treatment groups. The SOCs will be presented in alphabetical order, and the PTs will be presented in alphabetical order within each SOC.

The following summaries of adverse events will be generated:

- All TEAEs
- Treatment-emergent serious adverse events (SAEs)
- Treatment-emergent severe adverse events
- TEAEs with a reasonable possibility of being related to study drug

- TEAEs leading to discontinuation of study drug
- TEAE leading to death

Subjects reporting more than one adverse event for a given MedDRA preferred term will be counted only once for that term (most severe incident for the severity tables and most related incident for the relationship tables). Subjects reporting more than one type of adverse event within a SOC will be counted only once for that SOC. Subjects reporting more than one type of adverse event will be counted only once in the overall total.

10.2.1.3 TEAEs by Maximum Severity

[figure not shown]
TEAEs will also be summarized by maximum severity by treatment groups. If a subject has an AE with an unknown severity, then the subject will be counted in the severity category of unknown, even if the subject has another occurrence of the same event with a severity present. The only exception is if the subject has another occurrence of the same AE with the highest CTCAE grade; in this case, the subject will be counted under the highest CTCAE grade for the term in question.

10.2.1.4 TEAEs by Relationship

TEAEs will also be summarized by relationship to upadacitinib, adalimumab and placebo, as assessed by the investigator, by treatment groups. If a subject has a TEAE with an unknown relationship, then the subject will be counted in the relationship category of "unknown," even if the subject has another occurrence of the same event with a relationship present. The only exception is if the subject has another occurrence of the same TEAE with a relationship assessment of "reasonable possibility." In this case, the subject will be counted under the "reasonable possibility" category.

10.2.1.5 Frequent (≥ 2%) Adverse Events and Reasonably Possibly Related Adverse Events by System Organ Class and Preferred Term

TEAEs and reasonably possibly related AEs occurring for more than 2% of the subjects in any of the treatment groups will be summarized by SOC and PT separately.

10.2.1.6 Adverse Events of Special Interest

The Adverse Events of Special Interest (AESI) categories will be summarized and presented by treatment groups in overview as well as using SOC and PT. The AESI categories will be identified by the following search criteria per Standard MedDRA Queries (SMQs)/Company MedDRA Queries (CMQs) in Table 11 below. Adjudicated cardiovascular events will be summarized and presented by treatment group using the CAC adjudicated categories.

[figure not shown]

Table 11. AESI for Upadacitinib with SMQs/CMQs/PTs Searches

AESI	Type of MedDRA Query	Broad or Narrow Search	SMQ/CMQ Search Criteria
Serious Infections	CMQ		"Infections" - Subset for SAEs
Opportunistic Infection excluding Tuberculosis and Herpes Zoster	CMQ		"Opportunistic Infection excluding Tuberculosis and Herpes Zoster"
Possible Malignancy	SMQ	Narrow	"Malignancies"
Malignancy	SMQ	Narrow	"Malignant tumours"
Non-Melanoma Skin Cancer (NMSC)	SMQ	Narrow	Skin Malignant tumours (Narrow SMQ) removing Melanoma CMQ
Malignancy excluding NMSC			"Malignant tumours" SMQ (Narrow) removing NMSC output
Lymphoma	SMQ	Broad	"Malignant Lymphomas"
Hepatic Disorder	SMQ	Narrow	"Drug Related Hepatic Disorders"
Adjudicated Gastrointestinal Perforations	Based on adjudicated results (the identification of events to be adjudicated are described in the GI Perforation charter)		
Anemia	CMQ		"Non-Hemolytic and Non-Aplastic Anemias"
Neutropenia			"Hematological Toxicity – Neutropenia"
Lymphopenia	CMQ	"Hematological Toxicity – Lymphopenia"	
Herpes Zoster	CMQ		"Herpes Zoster"
Creatine Phosphokinase (CPK) Elevation	PT		Search only for the PT of "Blood creatine phosphokinase increased"
Renal Dysfunction	SMQ	Narrow	"Acute Renal, Failure"
Active Tuberculosis	CMQ		"Active Tuberculosis"

[figure not shown]

Table 11. AESI for Upadacitinib with SMQs/CMQs/PTs Searches (Continued)

AESI	Type of MedDRA Query	Broad or Narrow Search	SMQ/CMQ Search Criteria
Adjudicated cardiovascular events	Output from CAC		
MACE*			
Cardiovascular Death			
Non-fatal Myocardial Infarction			
Non-fatal Stroke			
Other Adjudicated Cardiovascular Events			
Undetermined/Unknown Cause of Deaths			
Adjudicated Thrombotic Events	Output from CAC		
VTE**			
Deep Vein Thrombosis			
Pulmonary Embolism			
Other Venous Thrombosis			
Arterial Thromboembolic Events (non-cardiac, non-neurologic)			

CAC = Cardiovascular Adjudication Committee; CMQ = company MedDRA query; PT = preferred term; SMQ = standard MedDRA query

- * MACE; Major Adverse Cardiovascular Events, defined as cardiovascular death, non-fatal myocardial infarction and non-fatal stroke.
- ** VTE: Venous thromboembolic events, defined as deep vein thrombosis (DVT) and pulmonary embolism (PE) (fatal and non-fatal).

Additional AEs may be considered for tabulation/summary based on recommendations from Clinical and Safety as deemed appropriate.

10.2.2 Analysis of Long-Term Adverse Event Rates

Long-term adverse events will be analyzed using event rates adjusted by cumulative exposure and will be based on the actual treatment received at the time of AE occurrence. For subjects switched from upadacitinib 30 mg QD to upadacitinib 15 mg QD, adverse events and exposure to upadacitinib 30 mg QD will be censored at the time of dose switch; subsequent adverse events and exposure starting the day of first dose of upadacitinib 15 mg QD will be summarized under separate groups. The detailed treatment groups including the handling of dose switch, are described in Section 8.1.

Exposure-Adjusted Event Rate (EAER)

To adjust for potentially different follow-up time between treatment groups, EAER will be provided. For the purpose of event rate calculation, the numerator will be the total number of AEs reported for the event (i.e., a subject can contribute more than one event to the numerator) and the denominator will be the total exposure time among subjects under the treatment group. The number of AEs reported (numerator), the total number of years of study drug exposure (denominator), and the exposure-adjusted AE event rate per 100 patient-years, calculated as ([numerator/denominator])*100, will be presented for each treatment group. The EAER will be the main approach to evaluate AEs in the long-term analysis.

The exposure adjusted incidence rate (censored at the time of first event) may be conducted for selected AESI endpoints as appropriate for long-term analysis.

10.2.2.1 Overview of Adverse Events Rates per 100 Patient-Years of Study Drug Exposure

An overview of AEs per 100 patient-years of study exposure will be presented by treatment group for the following AE categories.

- All TEAEs
- Treatment-emergent serious adverse events (SAEs)
- Treatment-emergent severe adverse events

- TEAEs reasonably possibly related to study drug
- TEAEs of special interest
- TEAEs leading to discontinuation of study drug
- TEAE leading to death
- Deaths (includes all deaths treatment-emergent and non-treatment-emergent)

In the AE overview summary, any event with an unknown severity will be considered as severe and any AE with an unknown relationship will be considered as having "reasonable possibility" of being related to study drug. Additional AEs may be considered for tabulation/summary based on recommendations from Clinical and Safety as deemed appropriate.

[figure not shown]
10.2.2.2 Adverse Events Rates per 100 Patient-Years of Study Drug Exposure by SOC and PT

For each treatment group, the TEAE rate per 100 patient-years of exposure will be calculated overall, for each SOC and each PT, for each of the following events:

- All TEAEs
- Treatment-emergent serious adverse events (SAEs)
- Treatment-emergent severe adverse events
- TEAEs with a reasonable possibility of being related to study drug
- TEAEs leading to discontinuation of study drug
- TEAE leading to death

10.2.2.3 Adverse Events of Special Interest Rates per 100 Patient-Years of Study Drug Exposure

The Adverse Events of Special Interest (AESI) categories will be summarized and presented for each treatment group in overview as well as using SOC and PT. The AESI categories will be identified per Standard MedDRA Queries (SMQs)/Company MedDRA

Queries (CMQs). Adjudicated cardiovascular events will be summarized and presented by treatment group using the CAC adjudicated categories.

10.2.2.4 Listing of Serious Adverse Events (Including Deaths) and Adverse Events Leading to Study Drug Discontinuation

All serious adverse events (SAEs), deaths, and adverse events leading to discontinuation of study drug will be listed.

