• Subject develops a gastrointestinal perforation, defined as acute, spontaneous perforation of the gastrointestinal tract that requires inpatient medical care or urgent surgical intervention (other than appendicitis or mechanical injury).

[figure not shown]
- Confirmed diagnosis of deep vein thrombosis, pulmonary embolus or noncardiac, non-neurologic arterial thrombosis
- Subject develops a major cardiovascular event (MACE: acute myocardial infarction or stroke)
- Subject develops a new ECG change considered clinically significant and with reasonable possibility of being related to study drug

Subjects will have adalimumab study drug treatment discontinued immediately if any of the following occur:

- Subject develops new or worsening symptoms of congestive heart failure
- Subject is diagnosed with lupus-like syndrome, multiple sclerosis, or demyelinating disease.

In order to minimize missing data for safety and efficacy assessments, subjects who prematurely discontinue study drug treatment should continue to be followed for all regularly scheduled visits as outlined in Appendix C, and adhere to all study procedures except for dispensing study drug, annual TB testing, PK sample collection, and blood sample collection for optional exploratory research and validation studies unless they have decided to discontinue the study participation entirely (withdrawal of informed consent). In addition, all future rescue and efficacy driven discontinuation criteria no longer apply. Subjects should be advised on the continued scientific importance of their data even if they discontinue treatment with study drug early.

If a subject is discontinued from study drug, the procedures outlined for the PD Visit should be completed as soon as possible, preferably within 2 weeks of the last dose of study drug, and preferably prior to the initiation of another therapy. In addition, if subject is willing, 30-day follow-up visit (or phone call if a visit is not possible) may occur to determine the status of any ongoing AEs/SAEs or occurrence of any new AEs/SAEs. For subjects on subcutaneous study drug, if the subject is willing, a 70-day follow-up phone call may occur to determine the status of any ongoing AEs/SAEs, the occurrence of any new AEs/SAEs, and medications used to treat AEs/SAEs. The follow-up visit/phone call

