8.0 Study Drug Exposure and Compliance

8.1 Study Drug Exposure

For short term up to Week 24, the duration of exposure to study drug will be summarized for the safety analysis set by the randomized treatment groups.

For long term, the duration of exposure to study drug will be summarized for the safety analysis set by the following groups.

1. Upadacitinib 15 mg QD

This includes upadacitinib 15 mg QD exposure from subjects starting on upadacitinib 15 mg QD and subjects switching from placebo to upadacitinib 15 mg QD.

2. Upadacitinib 30 mg QD

This includes upadacitinib 30 mg QD exposure from subjects starting on upadacitinib 30 mg QD and subjects switching from placebo to upadacitinib 30 mg QD. Exposure is censored at time of dose switch from upadacitinib 30 mg QD to upadacitinib 15 mg QD.

3. Upadacitinib 15 mg QD switched from upadacitinib 30mg QD

This includes Upadacitinib 15 mg QD exposure from subjects who switched dose from upadacitinib 30 mg QD to upadacitinib 15 mg QD.

4. Adalimumab 40 mg EOW

Exposure to upadacitinib and placebo is defined as last dose date minus first dose date plus 1 day. Exposure to adalimumab is defined as last dose date minus first dose date plus 14 days.

Starting with Amendment 6.01 (for Japan) and Amendment 7 and 7.01(for global), subjects receiving upadacitinib 30 mg QD will be switched to receiving upadacitinib 15

mg QD. Exposure to upadacitinib 30 mg QD (Groups 2) will be censored prior to the day subject received the first dose of upadacitinib 15 mg QD, and subsequent exposure to upadacitinib 15 mg QD will be summarized under separate groups (Groups 3).

The duration of exposure to study drug will be summarized for each group as specified above, with the number of subjects, mean, standard deviation, median, minimum and maximum values. In addition, the number and percentage of subjects exposed to study drug will be summarized for the following cumulative duration intervals.

- ≥ 2 weeks
- ≥ 1 month
- \geq 3 months
- \geq 6 months
- ≥ 9 months
- ≥ 12 months
- ≥ 18 months
- ≥ 2 years
- ≥ 2.5 years
- ≥ 3 years
- ≥ 3.5 years
- \geq 4 years
- ≥ 4.5 years

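### The long-term all-deaths rate counts deaths after study drug is stopped but divides by on-drug time only, so it is inflated within each arm

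*SAP*

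**What the plan says.** SAP Section 10.2.2 defines the long-term exposure-adjusted event rate. For each category "the numerator will be the total number of AEs reported for the event", and "the denominator will be the total exposure time among subjects under the treatment group". The same paragraph describes the second quantity as "the total number of years of study drug exposure (denominator"). Events are attributed to the treatment being received when they occur.

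SAP Section 8.1 sets the length of exposure: "Exposure to upadacitinib and placebo is defined as last dose date minus first dose date plus 1 day", and "Exposure to adalimumab is defined as last dose date minus first dose date plus 14 days".

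SAP Section 10.2.2.1 lists the rows of the rate overview. The last is "Deaths (includes all deaths treatment-emergent and non-treatment-emergent"). The row above it is treatment-emergent events leading to death.

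On follow-up, Protocol Section 5.4.1 says that "subjects who prematurely discontinue study drug treatment should continue to be followed for all regularly scheduled visits", except those who withdraw consent. Section 5.1 makes staying in the study the subject's choice. Section 6.1.4 has serious and non-serious events collected for the rest of participation in those who stay.

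SAP Section 10.1 calls for long-term comparisons of upadacitinib with adalimumab on the adverse event overview, as a difference with a 95% confidence interval.

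**The concern.** A rate per patient-year is interpretable only if events and time are counted over the same period. In this row they are not. A death long after the last dose counts, but none of the survival time between the end of exposure and that death does. The row then depends on how many subjects stop drug and how long they stay afterwards, as well as on mortality.

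Off-drug follow-up is part of the design: from Week 36, non-response at two consecutive visits leads to discontinuation of study drug (Protocol Section 5.1). A subject who stops at Week 36 and stays to Week 260 is followed off drug for (260 − 36) × 7 / 365.25 = 4.3 years.

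The attribution rule has a related gap. A subject who has stopped drug is receiving no study treatment at death, so the rule in Section 10.2.2 gives no group.

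Mortality against a TNF blocker is a question the protocol itself raises. Section 3.2 cites the higher mortality seen with another JAK inhibitor and says an increased risk cannot be fully excluded for others in the class.

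**Working it through.** The documents give no rate, death count or patient-year total for this row, so there is no stated figure to reproduce. The check has three steps.

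**1. Where exposure ends.** For upadacitinib, last minus first plus 1 day ends on the day of the last dose. For adalimumab, plus 14 days ends 13 days after the last injection. The all-deaths row has no upper time limit in any arm.

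**2. Inflation within an arm.** Let E be mean exposure in years, d the share of subjects who discontinue and F their mean off-drug follow-up in years. Assume the same constant death rate λ on and off drug. For N subjects, expected deaths are λN(E + dF) and the SAP denominator is NE. The reported rate is therefore λ(1 + dF/E). The documents give none of E, d or F. The assumed ranges are E 2 to 4 years, d 10% to 40% and F 0.25 to 2 years.

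| E (years) | d | F (years) | 1 + dF/E |
|---|---|---|---|
| 4 | 10% | 0.25 | 1.006 |
| 2 | 10% | 0.25 | 1.012 |
| 3 | 25% | 1 | 1.083 |
| 3 | 40% | 1 | 1.133 |
| 3 | 25% | 2 | 1.167 |
| 2 | 40% | 2 | 1.400 |

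The middle case is 1 + 0.25 × 1 / 3 = 1.083, about 8%. The range is about 1% to 40%.

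**3. Effect on upadacitinib versus adalimumab.** With equal true death rates, E = 3 and F = 2 in both arms, the reported ratio is (1 + d_U × 2/3) / (1 + d_A × 2/3), where d_U and d_A are the shares discontinued on upadacitinib and adalimumab:

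- 25% in both arms: 1.000
- 25% upadacitinib, 35% adalimumab: 1.167 / 1.233 = 0.946
- 35% upadacitinib, 25% adalimumab: 1.233 / 1.167 = 1.057

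The within-arm inflation cancels when the arms behave alike. When they differ, its sign follows whichever arm has more off-drug time.

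**The case against.** The plan has other mortality outputs. Treatment-emergent events leading to death have their own row, are tabulated again by organ class and preferred term (Section 10.2.2.2), and all deaths are listed (Section 10.2.2.4). The all-deaths row is openly labelled, and the long-term comparisons carry no decision rule. All of this stands and limits the harm, but it does not correct the all-deaths rate. Section 10.2.2.1 does say study exposure in its sentence, but its heading, Section 10.2.2 and Appendix E all mean study drug exposure.

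Large inflation figures are also open to challenge, because staying after stopping drug is optional. If 30% stop at 2 years and all stay 3 more, off-drug time is 0.3 × 3 = 0.9 and on-drug time 0.7 × 5 + 0.3 × 2 = 4.1, giving 22%. That assumes no stopper leaves, so it is not a central estimate.

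A reader might infer that the ordinary adverse event rates are wrong in the same way and favour upadacitinib. Treatment-emergent events are counted "no more than 30 days after the last dose of upadacitinib and placebo, and 70 days after the last dose of adalimumab", which leaves 30 − 0 = 30 uncovered days for upadacitinib and 70 − 13 = 57 for adalimumab. The effect is small. At a mean exposure of 3 years (1,095.75 days), with a full tail for every subject, inflation is 1 + 30/1,095.75 = 1.027 and 1 + 57/1,095.75 = 1.052, a ratio of 0.977. If a quarter of subjects have a tail, the ratio is 0.994. Tails are absent for subjects still on drug at a data cut and for 30 mg subjects censored at the dose switch. The metric is conventional and labelled as per year of drug exposure, so a different denominator there is a preference.

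**Conclusion.** The point holds for the all-deaths row only. As written, that row divides deaths from an unlimited period by time that stops at or shortly after the last dose, and no other section supplies a matching denominator or a group for off-drug deaths. The rate is inflated within each arm, by about 8% in the middle case and about 1% to 40% over the assumed ranges. These figures rest on assumed exposure, discontinuation and off-drug follow-up, and on equal hazard on and off drug.

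A reader might go further and conclude that the mortality comparison is biased for or against upadacitinib. The documents do not support that: the window is unbounded in every arm, and nothing shows that discontinuation or off-drug follow-up differs. The shift of about 5% in step 3 comes from an assumed 10-point difference in discontinuation and reverses when the arms are swapped.

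**What to change.** In SAP Section 10.2.2.1, for the all-deaths row only:

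- Divide by on-study person-years, from first dose to death, end of participation or data cut, or report the row as counts without a rate.
- State that an off-drug death, and its off-drug person-time if a rate is kept, belongs to the last treatment received.
- Keep the drug-exposure denominator for treatment-emergent events leading to death.

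Extending at-risk time for treatment-emergent events to the 30- or 70-day window is at most an optional sensitivity analysis.

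The cost is a few lines of SAP text and, if the rate is kept, a second denominator built from dosing, death and participation dates already collected. The table departs slightly from the present layout. SAP Section 11.1 says version 4.0 applies only to future long-term reporting, so completed primary and Period 1 results are unaffected.

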10.3 Analysis of Laboratory Data

10.3.1 Variables and Units

All laboratory parameters to be collected in this study are listed below. Laboratory parameters will be reported using the standard international (SI) units.

[figure not shown]

Table 12. List of Laboratory Variables

Bicarbonate

Laboratory Variables	
Hematology	
White Blood Cell (WBC) Count	
Red Blood Cell (RBC) Count	
Hemoglobin	
Hematocrit	
Platelets count	
Neutrophils	
Basophils	
Eosinophils	
Lymphocytes	
Monocytes	
Bands	
Chemistry	
Total Bilirubin	
Alkaline Phosphatase (ALP)	
Aspartate aminotransferase (AST)	
Alanine aminotransferase (ALT)	
Total Protein	
Albumin	
Glucose	
Triglycerides	
Blood Urea Nitrogen (BUN)	
Creatinine	
Sodium	
Potassium	
Calcium	
Inorganic Phosphorus	
Creatine Phosphokinase (CPK)	
Chloride	

[figure not shown]

Table 12. List of Laboratory Variables (Continued)

[figure not shown]
Laboratory Variables	
Chemistry (Continued)	
Cholesterol	
LDL cholesterol	
HDL cholesterol	
LDL/HDL ratio	
Cholesterol/HDL ratio	
Urinalysis	
Specific Gravity	
рН	
Protein	
Glucose	
Ketones	
Blood	
Microscopic Examination (if needed)	
Urobilinogen	
Bilirubin	
Leukocytes	
Nitrites	
Other	
hs-CRP	
ESR	

10.3.2 Analysis of Laboratory Data by Week 24

The laboratory data will be summarized by the "as treated" treatment groups (Upadacitinib 15 mg QD, Upadacitinib 30 mg QD, ADA 40 mg EOW and combined placebo groups).

